## 5.8 End-of-Study Definition

The end of the study is defined as the date of the last visit of the last participant in the study. The last study visit is at Day 90, when patient attends for colposcopy and standard of care LLETZ. A participant is considered to have completed the study if the participant has completed all periods of the study including the last visit as shown in the Schedule of Assessment.

# 6. Clinical Evaluation, Laboratory Tests, Follow-Up

## 6.1 Before treatment start

The following information will be recorded for all subjects up to 7 days prior to starting study treatment on D1(-7 days):

- Demographic details: Date of consent, enrolment, age, ethnicity, HPV vaccination status
- Clinical data: symptomatology, weight, height, vital signs
- Colposcopy findings (within 28 days of study commencement)
- Histology: routine histological grading (within 28 days of study commencement)
- HPV DNA oncotyping (within 28 days of study commencement)
- Concomitant medication: all non-study drugs taken will be recorded

### D1 of study

- Baseline safety blood tests full blood count (FBC), Urea and Elelctrolytes (U&E), Liver Function Tests (LFTs) will be conducted at D1
- Baseline study blood tests (plasma, Peripheral Blood Mononuclear Cell (PBMC)) will be collected at D1
- Vaginome and gut microbiome samples will be collected at D1
- Quality of Life Tool (European Quality of Life-5 Dimensions (EQ-5D))

## 6.2 During treatment

### D7, D14, D22, D36, D43, D57

- Telephone consultation on D7, D36, D57
- Clinical Assessment on D14, D22, D43
- Speculum examination on D22,D43
- Concomitant medication on D14, D22, D43

- Patient self reported adverse events
- Safety blood test – FBC, U&E, LFT on D14, D22, D43,
- Study blood tests (plasma & PBMC) on D14
- Quality of Life Tool (European Quality of Life–5 Dimensions (EQ-5D)) D7, D14, D22, D43

### **6.3 After the end of treatment (Follow-up)**

Following the end of IMP treatment x 3 cycles, patients will undergo the following:

#### **Day 64 (+ 3 days)**

- Clinical Review
- Speculum examination
- Safety blood test – FBC, U&E, LFT
- Study blood tests (plasma & PBMC)
- HPV DNA oncotyping
- Vaginome and gut microbiome samples
- Quality of Life Tool (European Quality of Life–5 Dimensions (EQ-5D))

#### **Day 90 (+ 14 days)**

- Clinical Assessment
- Safety blood test – FBC, U&E, LFT
- Study blood test (plasma & PBMC)
- Colposcopy & endocervical biopsy
- HPV DNA oncotyping
- Vaginome and gut microbiome sampling
- Large Loop Excision Transformation Zone
- Quality of Life Tool (European Quality of Life–5 Dimensions (EQ-5D))

## 6.4 Summary table

Study Procedures	Screening prior to study entry	D1 Clinical review prior to start of medication	D7 Telephone consultation	D14 Clinical Review	D22 Clinical Review	D36 Telephone consultation	D43 Clinical Review	D57 Telephone consultation	D64 (+3 days) Clinical Review	D90 (+14 days) Clinical Review
Consent	X									
Medical History	X	X		X	X		X		X	X
Clinical Examination	X	X			X		X		X	X
Telephone consultation review			X			X		X		
Toxicity Assessment			X	X	X		X		X	X
Concomitant medication check		X	X	X	X		X		X	
Patient self-reported events (diary card)			X	X	X		X		X	X
Vital signs		X		X	X		X		X	X
Pregnancy Test		X								
Study medication check				X			X		X	
Safety Blood Test (FBC/renal/liver profile)		X		X	X		X		X	X
Study Blood test		X		X					X	X
Speculum examination					X		X		X	
Colposcopy examination + Cervical Biopsy		X								X
HPV Test		X							X	X
Vaginome + gut microbiome sample		X							X	X
Large Loop Excision Transformation Zone (LETTZ)										X
QOL Tools (EuroQol EQ-5D)		X	X	X	X		X		X	X

## 7. Pharmacovigilance

### 7.1 Safety/Toxicity

All adverse events will be recorded; the investigator will assess whether those events are drug related (reasonable possibility, no reasonable possibility) and this assessment will be recorded in the database for all adverse events. This study will use the Common Terminology Criteria for Adverse Events (CTCAE V5.0) for adverse event reporting.

The AE monitoring period will commence on Day 1 of the study (start of IMP) till Day 90 of the study. Adverse events will be assessed by the worst grade and per CTCAE term from first dose until 30 days after last dose of study treatment.

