#### 1.2.2 Secondary outcome measures

- HPV DNA viral clearance at Day 90.
  - Viral clearance will be defined as absence of HPV genotype (s) detected at baseline.
- Vaginome and gut microbiome at Day 1, Day 64 and Day 90.
  - Changes in vaginome and gut microbiome will be compared between Day 1, Day 64 and Day 90.
- Serious Adverse Events at Day 90 using Common Toxicity Criteria (CTCAE V5.0).
  - Safety assessment will be based on patients who received at least one dose of IMP.
- Tolerability assessment will be based on the percentage of subjects that complete the designated dosing regime.

- Patient quality of life using the European Quality of Life–5 Dimensions (EQ-5D) quality of life tool Day 1, Day 7, Day 14, Day 22, Day 43, Day 64 and Day 90.

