**SERIOUS ADVERSE EVENTS SHOULD BE IMMEDIATELY REPORTED ACCORDING TO THE PROCEDURE DETAILED IN THIS PROTOCOL.**

Adverse Event (AE) — Any untoward medical occurrence in a patient or clinical investigation subject administered a pharmaceutical product and which does not necessarily have to have a causal relationship with this treatment.

An adverse event (AE) can therefore be any unfavourable and unintended sign (e.g. an abnormal laboratory finding), symptom or disease temporally associated with the use of a medicinal product, whether or not considered related to the medicinal product.

Pre-existing conditions should only be reported as an adverse event if the condition worsens by at least 1 CTCAE grade. As the IMP has a short half-life, we would expect drug clearance within 24 hours of stopping the IMP.

As part of pharmacovigilance, adverse event data will be collected from the day 1 of IMP dose until 30 days following the end of the IMP treatment schedule.

Adverse Reaction (AR) — All noxious and unintended responses to a medicinal product related to any dose should be considered adverse drug reactions.

Serious Adverse Event (SAE) or Serious Adverse Reaction (SAR) — *any untoward medical occurrence that at any dose:*

- Results in death,
- Is life-threatening,
- Requires inpatient hospitalisation or prolongation of existing hospitalisation,
- Results in persistent or significant disability/incapacity or
- Is a congenital anomaly/birth defect.

Medical and scientific judgement should be exercised in deciding whether expedited reporting is appropriate in other situations, such as important medical events that may not be immediately life-threatening or result in death or hospitalisation but may jeopardise the patient or may require intervention to prevent one of the other outcomes listed in the definition above. These should also usually be considered “serious”.

Suspected Unexpected Serious Adverse Reaction (SUSAR) — an Adverse Reaction which is classed in nature as both serious and unexpected

An ‘Unexpected Adverse Reaction’ is when both the nature and severity of the event is not consistent with the reference safety information available for the IMP in question.

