### **10.1.1 Interim analyses / Decision rules**

An interim analysis reviewing feasibility and tolerability will be performed once 10% (n = 3) and 50% (n = 14) of patients have completed their day 90 assessments. No early conclusions will be drawn.

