#### **Periods**

- "Baseline" is defined as the period from before study entry to first day of protocol treatment administration. For patients who never started treatment, the baseline period is assumed to end on the day of enrolment.
- "On treatment" is defined as the time on study after baseline (i.e., starting on the first day of protocol treatment administration) to and including 30 days after the day of last protocol treatment administration.
- "Follow-up period" is defined as the period that follows the on-treatment period until the end of the follow up. For patients who never started treatment, the follow-up period is assumed to start on the day of enrolment.

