#### **10.2.3.1 Safety analyses**

Tables on AEs will report

- all AEs irrespective of their relationship to treatment
- the AEs related to the treatment (excluding those declared not reasonably possibly related to the treatment, but including those with relationship not assessable).

The worst grade of the AEs per patient and per CTCAE term over each period will be tabulated by treatment arm. The percentage of patients on each treatment arm presenting severe treatment-related AE (grade  $\geq 3$ ), of patients reported to have died of toxicity and that of patients who stopped treatment due to toxicity will also be calculated and the 95% confidence interval will be presented.

For the reporting of SAEs:

- the study safety overview table will list the number of reported SAE terms, SAR terms and SUSAR terms per treatment arm and the number of reported death and toxic death cases;
- line listings of SAEs and of SARs will be provided;
- the number of SAEs and SARs per System Organ Class and Preferred Term will be tabulated

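### The adverse-event end dates in 7.1 and 7.3 do not agree with each other, and the 7.1 worst-grade cut-off stops where the follow-up part of the 10.2.3.1 table begins

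*Protocol*

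**What the plan says.** Two consecutive sentences of section 7.1 set different ends. The first reads: "The AE monitoring period will commence on Day 1 of the study (start of IMP) till Day 90 of the study". The second assesses events by worst grade and "per CTCAE term from first dose until 30 days after last dose of study treatment". The same section applies CTCAE v5.0 to adverse-event reporting without a time limit.

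Section 7.3 gives a third end: "adverse event data will be collected from the day 1 of IMP dose until 30 days following the end of the IMP treatment schedule". It does not say whether the schedule ends with the last tablet, with the last treatment break, or with the individual patient's own last dose.

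In section 10.2.3 (Periods), the on-treatment period runs "to and including 30 days after the day of last protocol treatment administration". The follow-up period "is defined as the period that follows the on-treatment period until the end of the follow up". Section 10.2.3.1 then requires: "The worst grade of the AEs per patient and per CTCAE term over each period will be tabulated by treatment arm".

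Sections 1.2.2 and 10.2.4 set the SAE outcome at Day 90. Section 6.4 schedules toxicity assessments at D64 and at D90, the latter with a window of +14 days. Sections 5.1.5 and 5.3 keep patients who stop treatment early in follow-up.

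**The concern.** When adverse-event recording ends is an instruction to sites, and an analysis plan cannot restore events that a site did not record. Here a site has two end dates for collection, one of them undefined.

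The worst-grade cut-off raises a separate problem. It is tied to each patient's last dose, whereas the safety outcome is tied to a fixed day. Under section 5.1.5 a related Grade 3/4 reaction ends treatment, so those patients get the earliest cut-off. If it were applied as written, the worst-grade tables and the proportions with grade 3 or higher toxicity (10.2.3.1, and Toxicity assessments in 10.2.4, which states no window of its own) would cover unequal time, shortest in patients who stopped for toxicity.

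**Working it through.** **Inputs.** Three 21-day cycles, 14 days on and 7 days off (5.1.1, 5.4). Temporary discontinuations are not permitted (5.3). Final visit on Day 90, +14 days (6.3, 6.4).

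**Dosing days.** Cycles start on Days 1, 22 and 43, so dosing runs on Days 1–14, 22–35 and 43–56. The last scheduled dose is on Day 56. Cycle 3 with its break ends on Day 3 × 21 = 63. The next day, 63 + 1 = 64, matches the planned D64 visit, which supports this calendar.

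**Can a 30-day rule give the Day 90 of 7.1?** It would need a last dose on Day 90 − 30 = 60, which lies in the cycle 3 break. The two readings of 7.3 for the planned schedule are:
- schedule ends with the last dose: 56 + 30 = Day 86, which is 90 − 86 = 4 days short;
- schedule ends with the break: 63 + 30 = Day 93, which is 93 − 90 = 3 days beyond.

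Neither equals Day 90.

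**Worst-grade cut-off in 7.1 (last dose + 30).**

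| Last dose | Cut-off | Days from cut-off to Day 90 | Days from cut-off to a visit on Day 104 |
|---|---|---|---|
| Day 56 (full course) | 56 + 30 = 86 | 4 | 18 |
| Day 35 (end of cycle 2 dosing) | 35 + 30 = 65 | 25 | 39 |
| Day 14 (end of cycle 1 dosing) | 14 + 30 = 44 | 46 | 60 |

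Day 104 is 90 + 14, the latest final visit. The last column matters only for the follow-up table, because monitoring in 7.1 ends at Day 90.

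**Against the analysis periods.** The on-treatment period of 10.2.3 ends on the same days (86, 65, 44), and follow-up begins the day after. The overlap between the worst-grade window and the follow-up period is therefore 0 days in every row. Read literally, that part of the table has no input.

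**What the Day 90 visit still captures.** Assume it looks back to Day 64 (the protocol does not state the look-back). In a full-course patient Days 65–86, that is 86 − 64 = 22 days, lie inside the cut-off, and only onsets from Day 87 lie outside. The whole interval lies outside only if the last dose was on or before Day 64 − 30 = 34.

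**The case against.** The best defence is that the second sentence of 7.1 is a summary rule and does not forbid grading. It uses the terms of the tabulation rule in 10.2.3.1, its window equals the on-treatment period, and the same section records all events and applies CTCAE without a time limit. The 10.2.3.1 sentence also looks like template text: it speaks of treatment arms in a single-arm trial, and a baseline table would be almost empty too. This is plausible and limits the finding. It does not remove it, because 7.1 does not label the sentence in that way, and the 7.1 and 7.3 end dates still differ.

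A reader might infer more than the documents support:
- *The Day 90 toxicity assessment has no graded events.* Not so for a full course, where only onsets from Day 87 are affected.
- *The SAE outcome loses events for want of a grade.* Seriousness in 7.3 is defined by outcome, and the SAE outputs in 10.2.3.1 are counts, listings and tables by organ class and term. An SAE on Day 88 counts with or without a worst-grade entry.
- *The interim review is compromised.* It waits until the set share "of patients have completed their day 90 assessments", but tolerability is defined in 1.2.2 and 10.2.4 as completion of the dosing regimen, which this window does not touch.
- *Early stoppers lose 25 or 46 days of collected events.* That needs a site to read the 7.3 schedule as the patient's own last dose. Sections 5.3 and 6.4 and the first sentence of 7.1 point to Day 90.

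Section 7.4 also requires all deaths to be reported, and related SUSARs however late they occur. For a full course the disputed days lie about 30 days after the last dose, whereas 7.3 expects clearance within 24 hours.

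**Conclusion.** The inconsistency holds as a conflict of wording with a limited effect on the analysis. Collection ends on Day 90 under 7.1, and on Day 86 or Day 93 under 7.3 for a full course. The worst-grade window, read literally, contributes nothing to the follow-up table. It falls 4 days short of Day 90 after a full course, 25 days short after a last dose on Day 35, and 46 days short after a last dose on Day 14.

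These figures assume dosing on the planned calendar and a literal reading of the grading sentence. The 25- and 46-day gaps apply to the worst-grade window, and to collection only on the less natural reading of 7.3. The protocol gives no frequency of early stopping, so the effect on event rates cannot be computed. Severity is minor to moderate.

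**What to change.** In 7.1 and 7.3 state a single window for collecting and CTCAE-grading AEs and SAEs: first dose to Day 90, for every patient who took at least one dose, whenever treatment stopped. Count the SAE outcome to Day 90 in all patients. In 7.1, label last dose plus 30 days as the on-treatment analysis period of 10.2.3 only, and say that later events, up to the final visit, are tabulated in the follow-up period.

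The cost is wording in two sections and a few more unrelated events on record. No visit is added, because 6.4 already schedules toxicity assessment at D64 and D90. Since the final visit may fall up to 14 days late, events after Day 90 would be observed for unequal times. Keeping them out of the Day 90 count deals with that.

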### 7.2 Reference Safety Information

A NeoART-CIN Reference Safety Information document based upon the Summary Product Characteristics for artesunate (WHOPAR., 2017) forms the Reference Safety Information for this study. Section 4.8 of the Summary Product Characteristics for artesunate (WHOPAR., 2017) lists the following potential side effects. The adverse events are listed by body system, organ class and absolute frequency. They are generally not based on adequately sized randomized controlled trials but on published literature data generated mostly during post-approval use. When frequency estimates are available they are defined as follows: very common ( $\geq 1/10$ ), common ( $\geq 1/100, < 1/10$ ), uncommon ( $\geq 1/1000, < 1/100$ ), rare ( $\geq 1/10,000, < 1/1000$ ), very rare ( $< 1/10,000$ ).

Very Common	Common	Uncommon	Rare
Blood and lymphatic disorders			
		Neutropenia Low reticulocyte count	
Cardiac disorders			
		Bradycardia	
Gastrointestinal disorders			
		Mild GI disturbances	
Hepato-biliary disorders			
		Elevated liver enzymes	
General disorders			
			Hypersensitivity (allergic reactions)

### 7.3 Serious adverse events

Serious adverse events or adverse drug reactions are defined by the *Malaysian Guideline for Safety Reporting of Investigational Products* and *Malaysian Guideline for Good Clinical Practice, 3rd Edition, Item 1.56*.

**SERIOUS ADVERSE EVENTS SHOULD BE IMMEDIATELY REPORTED ACCORDING TO THE PROCEDURE DETAILED IN THIS PROTOCOL.**

Adverse Event (AE) — Any untoward medical occurrence in a patient or clinical investigation subject administered a pharmaceutical product and which does not necessarily have to have a causal relationship with this treatment.

An adverse event (AE) can therefore be any unfavourable and unintended sign (e.g. an abnormal laboratory finding), symptom or disease temporally associated with the use of a medicinal product, whether or not considered related to the medicinal product.

Pre-existing conditions should only be reported as an adverse event if the condition worsens by at least 1 CTCAE grade. As the IMP has a short half-life, we would expect drug clearance within 24 hours of stopping the IMP.

As part of pharmacovigilance, adverse event data will be collected from the day 1 of IMP dose until 30 days following the end of the IMP treatment schedule.

Adverse Reaction (AR) — All noxious and unintended responses to a medicinal product related to any dose should be considered adverse drug reactions.

Serious Adverse Event (SAE) or Serious Adverse Reaction (SAR) — *any untoward medical occurrence that at any dose:*

- Results in death,
- Is life-threatening,
- Requires inpatient hospitalisation or prolongation of existing hospitalisation,
- Results in persistent or significant disability/incapacity or
- Is a congenital anomaly/birth defect.

Medical and scientific judgement should be exercised in deciding whether expedited reporting is appropriate in other situations, such as important medical events that may not be immediately life-threatening or result in death or hospitalisation but may jeopardise the patient or may require intervention to prevent one of the other outcomes listed in the definition above. These should also usually be considered “serious”.

Suspected Unexpected Serious Adverse Reaction (SUSAR) — an Adverse Reaction which is classed in nature as both serious and unexpected

An ‘Unexpected Adverse Reaction’ is when both the nature and severity of the event is not consistent with the reference safety information available for the IMP in question.

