**Possibly** — there is some evidence to suggest a causal relationship (e.g. the event occurred within a reasonable time after administration of the trial medication). However, the influence of other factors may have contributed to the event (i.e. the patient's clinical condition, other concomitant events).

**Unlikely** — there is little evidence to suggest there is a causal relationship (e.g. the event did not occur within a reasonable time after administration of the trial medication). There is another reasonable explanation for the event (e.g. the participant's clinical condition, or other concomitant treatments).

**Unrelated** — there is no evidence of any causal relationship.

**Not Assessable** — Note if this description is used the sponsor will assume the event is related to the IMP until follow up information is received from the investigator to confirm a definitive causality assessment.

Any SUSAR assessed as related to the IMP will need to be reported to the Sponsor irrespective of how long after IMP administration the reaction has occurred.

Expectedness should be based solely on the available Reference Safety Information (RSI) for the

IMP and will be described using following categories :

**Expected** — an AE that is classed in nature as serious and which is consistent with the information about the IMP listed in the RSI or clearly defined in this protocol.

**Unexpected** — an AE that is classed in nature as serious and which is not consistent with the information about the IMP listed in the RSI.

The completed AE Log will be sent to Sponsor upon request and/or every 2 months.

The Chief Investigator (CI) will respond to any SAE queries raised by the Sponsor as soon as possible. Follow up reports must continually be completed within acceptable time-frames and sent to the sponsor as detailed above until the reportable event is considered resolved.

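### Sections 7.3 and 7.4 define an unexpected reaction differently, so a serious GI reaction more severe than the listed one is a SUSAR under one section and not under the other

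*Protocol*

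**What the plan says.** Section 7.3 of the protocol defines a SUSAR as "an Adverse Reaction which is classed in nature as both serious and unexpected". It then defines an unexpected adverse reaction as arising "when both the nature and severity of the event is not consistent with the reference safety information" available for the product.

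Section 7.4 gives the categories to be used when expectedness is assessed. An event is unexpected if it is "an AE that is classed in nature as serious and which is not consistent with the information about the IMP listed in the RSI". It is expected if it is serious and is one "which is consistent with the information about the IMP listed in the RSI or clearly defined in this protocol". Neither category mentions severity.

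Section 7.2 says that the RSI is a trial-specific document based on the product characteristics for artesunate, and reproduces the side effects listed there. There are six: neutropenia, low reticulocyte count, bradycardia, GI disturbances, elevated liver enzymes and hypersensitivity. Only the GI entry has a severity attached: "Mild GI disturbances".

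The classification is used in two places. Section 7.4 requires SUSARs to go to the regulator and the ethics committee within 7 calendar days, and sets 15 calendar days to the regulator for serious unexpected reactions that are neither fatal nor life-threatening. In section 10.2.3.1, "the study safety overview table will list the number of reported SAE terms, SAR terms and SUSAR terms".

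**The concern.** The word *both* in section 7.3 makes the test conjunctive: nature and severity must each depart from the RSI. A known reaction in a more severe form departs on severity only, so it fails the test. Section 7.4 has no such requirement. Two assessors who each follow the protocol could therefore classify the same event differently, with different consequences for expedited reporting and for the SUSAR count.

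The events concerned are ones this trial has reason to watch. Section 5.1.8 asks for close safety surveillance because dosing is longer than in malaria: 3 cycles × 14 days = 42 dosing days, against an average of 3 to 5 days, which is 42/5 = 8.4 to 42/3 = 14 times as many. A listed reaction in a more severe form is one plausible signal of longer exposure, and it is the kind of event that the literal 7.3 wording leaves out.

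**Working it through.** The plan states no figure on this point, so the check is logical. Take an event that is serious and judged related to artesunate, and vary whether its nature and its severity are consistent with the RSI.

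| Nature vs RSI | Severity vs RSI | Section 7.3 (literal) | Section 7.4 |
|---|---|---|---|
| consistent | consistent | not unexpected | expected |
| not consistent | not consistent | unexpected, SUSAR | unexpected, SUSAR |
| consistent | not consistent | not unexpected, no SUSAR | unexpected, SUSAR |
| not consistent | no conflict | not unexpected, no SUSAR | unexpected, SUSAR |

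The sections agree in the first two rows and differ in the last two. The fourth row is not pressed here: a reaction that is not listed has no listed severity to be consistent with, so how the 7.3 test applies to it is open to argument. The point rests on the third row.

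**Does the third row occur with the protocol's own list?** The six entries fall into two groups.

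- *GI disturbances, listed as mild.* Suppose a participant is admitted to hospital with a severe, related GI reaction. The nature is listed and the severity is not. Under 7.3 only one of the two conditions is met, so the reaction is not unexpected and not a SUSAR. Under 7.4 a severe event is not consistent with an entry limited to mild, so it is unexpected and, being a serious reaction, a SUSAR.
- *The other five entries*, for example "Neutropenia Low reticulocyte count". None has a severity in section 7.2. Under 7.3 their nature is consistent, so they are not unexpected at any severity. Under 7.4 severe neutropenia may well be consistent with an entry that sets no limit, and hence expected. Section 7.4 also lets an event count as expected if the protocol defines it, and sections 5.1.5 and 5.2 already anticipate neutropenia of grade 3 or worse. The two sections may therefore agree on these terms. Whether they do depends on the RSI document itself, because "Expectedness should be based solely on the available Reference Safety Information (RSI) for the" product.

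The conflict is thus demonstrated for one of six listed terms and left open for five.

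**Expected number of events.** The table places GI disturbances in the uncommon class, at least 1/1000 and below 1/100. With at most 28 participants, the expected number with any GI disturbance runs from 28 × 0.001 = 0.028 to just under 28 × 0.01 = 0.28. This is only a rough guide. Section 7.2 says the frequencies mostly come from published post-approval data and not from adequately sized trials, and dosing here is longer.

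**The case against.** The strongest reply is that the 7.3 sentence is loosely drafted. Its verb is singular, and it may only mean that nature and severity are both to be considered. Section 7.4 is the working instruction for assessors, and it allows a severe GI reaction to be classed as unexpected. This is a fair account of what may have been intended. But *both* is explicit, the SUSAR definition in 7.3 relies on the same term, and nothing in the protocol corrects it. The reference to national guidelines at the start of 7.3 covers the definitions of serious adverse events and adverse drug reactions, not expectedness.

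A reader might also infer more than the protocol supports:

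- *That a more severe form of a listed reaction can never be a SUSAR in this trial.* This is true of the 7.3 sentence only. Section 7.4 provides another route.
- *That all six listed reactions can be unexpected under 7.4.* Section 7.4 does not name severity, five entries carry none, and the operative RSI document is not shown.
- *That severe reactions would escape safety oversight.* Under section 7.4 every serious event goes to the sponsor within 24 hours, and all deaths are reported to the sponsor. Section 10.2.3.1 line-lists all SAEs and SARs, and reports the percentages with related events of grade 3 or higher, toxic deaths and stops for toxicity. None of this depends on expectedness.
- *That the analysis section is also wrong.* Section 10.2.3.1 contains no definition of unexpected. It only counts what 7.3 and 7.4 deliver.

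**Conclusion.** The inconsistency is real and narrow. Sections 7.3 and 7.4 give different tests for the same classification, and on the protocol's own side-effect list they give opposite answers for a serious GI reaction more severe than mild. For the other five listed reactions the protocol alone does not settle whether they differ.

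The effect is on expedited reporting to the regulator and the ethics committee and on one count in the safety overview table. Events are not lost to the sponsor, and efficacy, error rates, power and sample size are untouched. With at most 28 participants the conflict may never arise. It should still be corrected, because the rule decides a time-limited regulatory report.

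This rests on a literal reading of 7.3, and on the assumption that the RSI document keeps the mild qualifier shown in section 7.2. If that document lists severities for more terms, more terms are affected.

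**What to change.** Use one definition in both places. In section 7.3, state that an adverse reaction is unexpected when its nature *or* its severity is not consistent with the RSI. In section 7.4, use the same wording for the unexpected category and its converse for the expected one, so that severity is named there too. Changing 7.3 alone would leave 7.4 silent on severity. Section 10.2.3.1 can stay as it is.

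While making the change, the sponsor should check which entries in the separate RSI document state a severity, since that determines how the new definition works for the other five terms.

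The cost is a short text amendment and possibly a few more expedited reports.
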